#### Non-Date Values

For sensitivity analyses of the primary efficacy endpoint, missing values will be imputed using multiple imputation (see Section 3.4.1). For the analyses of secondary and exploratory efficacy endpoints, no imputation will be made for missing values. Safety data will be used according to availability, with no imputation for missing data.

#### 3.1.6 Evaluation of Site Effect

This is a multi-center study. Sites will not be pooled for any planned inferential analysis but may be pooled for subgroup analysis to assess the heterogeneity of treatment effects among pooled sites. The final pooling algorithm, if needed, will be specified before treatment unblinding and will be provided as an addendum to the SAP. Additionally, a review of by-site effects will be performed in the context of data listing review.

#### 3.2 Analysis Populations

#### 3.2.1 Intent-to-Treat (ITT) Population

The Intent-to-Treat (ITT) Population will include all participants randomized into the study. Treatment classification will be based on the randomized treatment.

#### 3.2.2 Modified ITT (mITT) Population

The Modified ITT (mITT) Population will include all participants in the ITT Population who receive at least 1 dose of any study drug and have a Baseline value for the LDL-C assessment. Any efficacy measurement obtained during the Safety Follow-up Visit after a participant permanently discontinues the study drug or after a participant receives an excluded medication and/or procedure will be removed from the mITT analysis. Treatment classification will be based on the randomized treatment. The mITT Population will be used for the primary analysis of all efficacy endpoints.

#### 3.2.3 Per-Protocol (PP) Population

The Per-Protocol (PP) Population will include all participants in the mITT Population who have a Baseline value for the LDL-C assessment, have a Day 56 value for the LDL-C assessment, and who did not experience a major protocol deviation that potentially impacted the primary efficacy endpoint. Major protocol deviations will be defined in the Protocol Deviation Plan within the trial

master file to align with International Conference on Harmonization guidelines. The PP Population, along with the reason for exclusion, will be finalized prior to study unblinding. The PP Population will be a secondary population for analysis of the primary efficacy endpoint.

#### 3.2.4 PK Population

The PK Population will include all participants in the mITT Population who have sufficient blood samples collected for valid estimation of PK parameters.

#### 3.2.5 Safety Population

The Safety Population will include all participants who receive at least 1 dose of any study drug. Treatment classification will be based on the actual treatment received. The Safety Population will be the primary population used for the safety analyses.

#### 3.3 Subject Data and Study Conduct

#### 3.3.1 Subject Disposition

Subject disposition will be presented for all randomized participants. Counts and percentages of participants who are randomized, complete the study, complete the treatment, prematurely discontinue from the study, reasons for study discontinuation, and primary reason for early termination was due to COVID-19 will be summarized by treatment and overall. For each scheduled visit, counts and percentages of participants who do not complete the visit, partially complete the visit in-person, or complete the visit virtually will be summarized by treatment. The denominator for calculating percentages will be based on the number of randomized participants.

Data listings for subject disposition and exclusion and inclusion criteria violations will be provided.

#### 3.3.2 Protocol Deviations

Protocol deviations will be identified based on the clinical data as defined in the Protocol Deviation Plan. The Protocol Deviation Plan will define all protocol deviations as either CSR reportable or non-CSR reportable deviations. Counts and percentages of participants with CSR reportable protocol deviations by deviation category will be summarized by treatment and in total based on all randomized participants. A listing of CSR-reportable protocol deviations will be generated.

#### 3.3.3 Analysis Populations

Counts and percentages of participants in each analysis population will be summarized by treatment and in total based on all randomized participants. Reasons for exclusion from PP population will also be summarized.

#### 3.3.4 Demographic and Baseline Characteristics

Demographic and Baseline characteristics including age, race, ethnicity, sex, height, weight, body mass index, and stratification group (LDL-C value ≥100 or <100 mg/dL) will be summarized with descriptive statistics or counts and percentages of participant as appropriate by treatment and in total for the mITT Population. If they differ from the mITT Population, summaries will also be provided for the ITT Population, the PP Population and the Safety Population.

#### 3.3.5 Medical History

Medical history will be coded to system organ class and preferred term using the Medical Dictionary for Regulatory Activities (MedDRA) version 23.1. Counts and percentages of participants with medical history by system organ class and preferred term will be summarized by treatment and in total based on all randomized participants.

#### 3.3.6 Concomitant Medications

Medication start and stop dates that are recorded on the Prior & Concomitant Medications case report form will be used to determine whether the medications are prior or concomitant to the study treatment. Concomitant medications are defined as those used on or after the first dose of study treatment. Prior medications are defined as those used prior to and stopped before the first dose of study treatment. All prior and concomitant medication verbatim terms will be coded using the World Health Organization (WHO) Drug Dictionary (WHO Drug\_Sept 2020G B3). The numbers and percentages of participants taking prior and concomitant medications in each treatment and in total will be summarized by anatomical therapeutic chemical (ATC) class and preferred term for the Safety Population.

#### 3.3.7 Study Drug Exposure and Compliance

Participants' exposure to randomized study medication will be summarized with descriptive statistics for the Safety Population. Days of exposure is defined as:

date of last dose of study drug - date of first dose + 1

For those whose date of first dose from the initial blister card dispensed was not available, the date of randomization will be used to assign the date of first dose. For those who failed to provide the date of last dose of study drug, the earliest date between the end of treatment date and the date of end of study/early termination will be used.

A summary will be provided to display counts and percentages of participants in each treatment with exposure in the following categories: <4 weeks, 4 – <8 weeks, and 8+ weeks.

Summary statistics will be presented for percent overall compliance to study medication by treatment and in total. Counts and percentages of participants will also be tabulated by groups with overall compliance < 80%, 80% to 120%, and > 120%.

The percent overall compliance to study medication will be calculated as:

$$100 imes rac{number\ of\ actual\ tablets\ taken}{expected\ tablets\ taken}$$
 ,

Expected tablets taken =  $2 \times$  (the earliest date between the end of treatment date and the date of early termination – the date of randomization +1).

The number of actual tablets taken is the sum of number administered from each blister pack. If number administered from a blister pack is missing, the number administered is considered 16 for the compliance calculation.

A separate listing of derived exposure and compliance will be provided for all randomized participants.

#### 3.4 Efficacy Assessment

The mITT Population will be the primary population for the efficacy analyses. Efficacy will also be analyzed using the ITT Population and the PP Population as supportive analyses for selected endpoints.

LDL-C will be collected using the following two approaches:

- At each scheduled visit, LDL-C will be calculated using the Friedewald equation unless TG≥400mg/dL or LDL-C≤50 mg/dL; in both cases, LDL-C level will be measured directly by preparative ultracentrifugation (PUC), also referred to as beta quantification [LDL calculated, 2020].
- 2. In addition, at Baseline (Day 1) and at the end of the 8-week Treatment Period (Day 56), LDL-C will be measured for all patients by PUC.

#### 3.4.1 Primary Efficacy Endpoint

#### Primary Analysis

The primary efficacy endpoint is the percent change from Day 1 to Day 56 in LDL-C (as determined by approach 1) for each obicetrapib group compared to the placebo group. The percent change will be calculated from Baseline to each measurement taken at Day 28 and Day 56.

The percent change in LDL-C from Day 1 to Day 56 for each treatment is defined mathematically as  $\mu_j$ , where j stands for the jth treatment (j=0,1,2) and the subscript 0 refers to the placebo group. The hypotheses testing to the percent change in LDL-C from Day 1 to Day 56 is then defined statistically as following:

$$H_0$$
:  $\mu_i - \mu_0 = 0$ ,  $H_1$ :  $\mu_i - \mu_0 \neq 0$ , where  $j=1,2$ 

The primary efficacy analysis of the percent change from Day 1 to Day 56 in LDL-C will be performed using a mixed model for repeated measures (MMRM) approach. The analysis will include fixed effects for treatment, visit, and treatment-by-visit interaction, along with a covariate of the Baseline value as a continuous covariate. It is to note that randomization was stratified by categories of LDL-C value (≥100 or <100 mg/dL) only to ensure similar distribution of LDL-C values across all treatment. However, the MMRM model will include the original scale of the LDL-C value as a continuous covariate, not categorical.

The Restricted Maximum Likelihood estimation approach will be used with an unstructured covariance matrix. The least squares means, standard errors, and 2-sided 95% confidence intervals for each treatment group and for the pairwise comparisons of each dose of obicetrapib to the placebo group will be provided. Adjustment for multiple comparisons will be made using Dunnett's test in accordance with the power and sample size calculations utilized for the study.

The MMRM approach will include all available assessments of percent change in LDL-C from Baseline to Day 28 and Day 56. The model assumes the data are missing at random (MAR). If any data are missing, the model will use all information from the other time points to estimate the mean treatment difference at the given time point. No imputation of missing data will be performed for the primary efficacy endpoint analysis.

For participants who are withdrawn from the study because of the use of a prohibited medication, data occurring after the intercurrent event of prohibited medications use will be excluded from the

primary analysis. For participants who are withdrawn from the trial, data occurring after the intercurrent event of failure to adhere to treatment dosing will be excluded from the primary analysis. Failure to adhere to treatment dosing will be defined as study drug compliance <75% at the time of study withdrawal.

The MMRM analysis will be implemented using SAS® Proc Mixed. Example SAS code can be found below:

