4 SELECTION AND WITHDRAWAL OF PARTICIPANTS

4.1 Inclusion Criteria

Participants who meet all of the following criteria will be eligible to participate in the study:

- 1. Understanding of the study procedures, willingness to adhere to the study schedules, and agreement to participate in the study by giving written informed consent prior to screening procedures;
- 2. Men or women 18 to 75 years of age, inclusive, at the Screening Visit;
 - o Women may be enrolled if all 3 of the following criteria are met:
 - They are not pregnant;
 - They are not breastfeeding; and
 - They do not plan on becoming pregnant during the study;
 - O Women of childbearing potential must have a negative urine pregnancy test at the Screening Visit. Note: Women are not considered to be of childbearing potential if they meet 1 of the following criteria as documented by the Investigator:
 - They have had a hysterectomy or tubal ligation at a minimum of 1 cycle prior to signing the ICF; or
 - They are postmenopausal, defined as ≥1 year since their last menstrual period for women ≥55 years of age or ≥1 year since their last menstrual period and have a follicle-stimulating hormone (FSH) level in the postmenopausal range for women <55 years of age; and

 - O Women of childbearing potential must agree to use an effective method of avoiding pregnancy from screening to 90 days after the last visit. Men whose partners are of childbearing potential must agree to use an effective method of avoiding pregnancy from screening to 90 days after the last visit. Effective methods of avoiding pregnancy are contraceptive methods with a Pearl index of <1 used consistently and correctly (including implantable contraceptives, injectable contraceptives, oral contraceptives, transdermal contraceptives, intrauterine devices, diaphragm with spermicide, male or female condoms with spermicide, or cervical cap) or a sterile sexual partner;
- 3. Fasting LDL-C levels >70 mg/dL and TG levels <400 mg/dL at the Screening Visit; and
- 4. Currently receiving high-intensity statin therapy (atorvastatin 40 or 80 mg or rosuvastatin 20 or 40 mg) at a stable dose for 8 weeks prior to screening and intending to remain at the same stable dose throughout the study duration.

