#### 3.1.3 Definition of Baseline

Unless otherwise stated, Baseline will be defined as the last measurement prior to the first dose of study drug.

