Note: non-MONOTONE missing values TREATMENT = 0 (Placebo), 1 (5 mg obicetrapib), 2 (10 mg obicetrapib) LDLC BASE = LDL C Baseline value LDLC Day28 = LDL C value at Day 28 LDLC Day56 = LDL C value at Day 56 proc mi data=LDLC\_Wide seed=18032021 out=LDLC\_25MCMC nimpute=25; var TREATMENT LDLC base LDLC Day28 LDL Day56; mcmc impute=monotone chain=multiple; In the second step, the remaining monotone missing values will be imputed. Example SAS code to complete this step is shown below: \* MONOTONE missing values TREATMENT = 0 (Placebo), 1 (5 mg obicetrapib), 2 (10 mg obicetrapib) LDLC BASE = LDL C Baseline value LDLC\_Day28 = LDL\_C value at Day 28 LDLC Day56 = LDL C value at Day 56 proc mi data= LDLC\_25MCMC seed=810456 out= LDLC\_Mono nimpute=1 simple; monotone method=rea: var TREATMENT LDLC\_base LDLC\_Day28 LDL\_Day56; by \_Imputation\_; run; For each imputation dataset, the percent change from Baseline to Day 28 and Day 56 will be analyzed using similar MMRM approach. Then the parameter estimates will be combined using Rubin's method. Example SAS code to combine the parameter estimates is shown below: Note: MIANALYZE to combine imputations proc mianalyze parms(classvar=full)=mixLSM; class TREATMENT: modeleffects TREATMENT: ods output parameterestimates=mi\_LSM; proc mianalyze parms(classvar=full)=mixDIFF; class TREATMENT: modeleffects TREATMENT; ods output parameterestimates=minus\_mi\_DIFF; \* Sensitivity Analysis 2

In the second sensitivity analysis, the percent change from Day 1 to Day 56 in LDL-C, via approach 1, for the obicetrapib groups compared to the placebo group will be analyzed using an Analysis of Covariance (ANCOVA) model with fixed effects of treatment group and the Baseline LDL-C value as a continuous covariate. The least squares means, standard errors, and 2-sided 95% confidence intervals for each treatment group, for the pairwise comparisons of two obicetrapib will be provided. The treatment comparison will be performed using a 2-sided test at the  $\alpha$  = 0.05 level of significance. No imputation of missing data will be performed for this sensitivity analysis.

Example SAS code can be found below:

#### Sensitivity Analysis 3

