In the final sensitivity analysis, the percent change from Day 1 to Day 56 in LDL-C will be assessed where the LDL-C values will be measured by PUC. The percent change from Day 1 to Day 56 in LDL-C by PUC for the obicetrapib groups compared to the placebo group will be analyzed using an ANCOVA similar to the model described in the second sensitivity analysis. No imputation of missing data will be performed for this sensitivity analysis.

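### Does switching from Friedewald to ultracentrifugation at low LDL-C distort the primary percent change?

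*SAP*

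**What the plan says.** SAP 3.4 describes two ways of obtaining LDL-C. Approach 1 applies at each scheduled visit: "LDL-C will be calculated using the Friedewald equation unless TG≥400mg/dL or LDL-C≤50 mg/dL", in which case PUC is used. Approach 2 is additional: at Day 1 and Day 56, "LDL-C will be measured for all patients by PUC". Protocol Section 7 has the same arrangement, with the hybrid value as the LDL-C level and PUC as an extra measurement at Visits 2 and 4.

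SAP 3.4.1 bases the primary endpoint on approach 1, as the "percent change from Day 1 to Day 56 in LDL-C (as determined by approach 1"), and the model uses both post-baseline visits: "The MMRM approach will include all available assessments of percent change in LDL-C from Baseline to Day 28 and Day 56". The hypotheses compare each dose with placebo only. Sensitivity Analysis 2 is an ANCOVA of the "percent change from Day 1 to Day 56 in LDL-C, via approach 1". Sensitivity Analysis 3 is a similar ANCOVA in which "the LDL-C values will be measured by PUC".

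Entry (Protocol 4.1) requires "Fasting LDL-C levels >70 mg/dL and TG levels <400 mg/dL at the Screening Visit", and SAP 3.1.3 states that "Baseline will be defined as the last measurement prior to the first dose of study drug".

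**The concern.** Because of the entry limits, nearly every baseline is a Friedewald value. A Day 56 value at or below 50 mg/dL is a PUC value. No rule requires one method in both halves of a participant's ratio, and low values arise mainly in participants who respond to the drug. The endpoint therefore mixes two methods in proportions that differ by arm, while a single-method measure is planned for everyone at the two visits that define it.

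If the switch distorted the ratio, the size of the reported LDL-C reduction would be affected, and so would the comparison of 5 mg with 10 mg. Protocol 1.4 says the data will support dose selection.

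**Working it through.** **Inputs from the documents.** Difference 30 points, SD 15, 36 evaluable per group, two-sided 0.025 (SAP 2.2.4); switch at 50 mg/dL (SAP 3.4); Screening LDL-C above 70 mg/dL (Protocol 4.1).

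**The plan's own figure.** 30 / (15 × √(2/36)) = 8.49. Less the critical value 2.24 this leaves 6.24, so power is above 99.99%, consistent with the stated figure of more than 90%. The 95% half-width for a difference is 1.96 × 15 × √(2/36) = 6.9 points.

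**How often the methods mix.** From baseline b, reaching 50 mg/dL needs a change of 100 × (50/b − 1). Take normal changes with SD 15, mean 0 on placebo (assumed) and −30 on drug:
- b = 80: threshold −37.5%. Placebo Φ(−37.5/15) = 0.6%; drug Φ(−7.5/15) = 30.9%.
- b = 90: threshold −44.4%. Placebo Φ(−44.4/15) = 0.15%; drug Φ(−14.4/15) = 16.8%.

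So the mixing is real and one-sided. The question is whether it moves the estimate away from a single-method result.

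**Where the error comes from.** Let F0 and F1 be the Friedewald values at baseline and Day 56, and let PUC add d0 and d1. PUC throughout gives the ratio (F1 + d1)/(F0 + d0). Approach 1 gives (F1 + d1)/F0 if switched and F1/F0 if not.
- If the methods differ only at 50 mg/dL or below, d0 = 0 for a baseline above 50, and d1 = 0 whenever no switch occurs. Both forms then equal the PUC ratio, so the error is exactly zero.
- If the difference depends on level (assumed: 8 mg/dL at 60 or below, falling linearly to zero at 100) and F0 = 90, then d0 = 8 × 10/40 = 2. Switched, F1 = 45: approach 1 gives 53/90 − 1 = −41.1%, PUC gives 53/92 − 1 = −42.4%, error +1.3 points. Friedewald alone gives −50.0%, error −7.6. Not switched, F1 = 63, d1 = 8 × 37/40 = 7.4: approach 1 gives −30.0%, PUC gives 70.4/92 − 1 = −23.5%, error −6.5. The unswitched value carries the larger error.
- If the difference is a constant 8 and F0 = 90: switched, F1 = 45, approach 1 gives −41.1% and PUC 53/98 − 1 = −45.9%, error +4.8. Not switched, F1 = 63: −30.0% against 71/98 − 1 = −27.6%, error −2.4. The signs oppose and partly cancel in the mean.

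**Group means, by simulation.** All of the following are assumptions: usual LDL-C normal with mean 85, SD 20 or mean 95, SD 25; Screening above 70; within-person SD 0, 8 or 12; falls of 30, 40 or 50% with SD 15; PUC minus Friedewald of ±2, ±5 or ±8 mg/dL in the three shapes above. That makes 6 baselines × 18 offsets × 3 falls = 324 drug-placebo contrasts. Switching triggered by triglycerides was not modelled.

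| Assumed offset | Approach 1 minus PUC throughout, drug minus placebo (points) |
|---|---|
| Only at 50 or below (108 contrasts) | 0.00 |
| Constant, ±8 | at most 1.65 in size |
| Level-dependent, ±8, 30% fall (14-23% mixed) | −2.8 to +3.1 |
| Level-dependent, ±8, 50% fall (51-62% mixed) | −1.7 to +1.9 |
| Any shape, ±2 | at most 0.75 in size |

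In the level-dependent shape, which gives the largest errors, more switching goes with less error. Over all 324 contrasts approach 1 differs from PUC throughout by −2.8 to +3.1 points and Friedewald throughout by −6.6 to +7.0. Approach 1 is the further of the two in none.

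**Between the doses.** 10 mg minus 5 mg under approach 1 differs from PUC by at most 1.2 points if the true falls differ by 10 points, and by at most 2.2 if they differ by 20. The half-width is 6.9.

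**The case for a change.** The strongest case is that the headline figure stays on mixed methods when a single-method figure is available from samples already planned. Sensitivity Analysis 3 follows an ANCOVA tested at 0.05 with no Dunnett adjustment stated, so it does not replace the primary result. For 10 mg minus 5 mg, approach 1 was further from PUC than Friedewald throughout in 56 of 324 contrasts, so here the switch can add error. Using PUC at Day 56, with approach 1 at Day 28 only to support missing values, would keep the model form. In simulation that model stayed within 0.06 points of the complete-data PUC estimate with 5% missing at random, and within 0.32 with about 17% missing related to Day 28 response.

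The facts in this stand, but they do not make the plan wrong:
- The dose-to-dose contrast is not a primary hypothesis. A 20-point gap between doses also sits badly with Protocol 5.2, which reports near-maximal effects at 5 mg.
- PUC for everyone exists at one post-baseline visit only. The alternative model has two baselines and a different measure at each visit, so the visit effect is confounded with the method.
- Early-termination lipids assigned to Day 56 (Days 43-71, SAP 3.1.2) have no stated PUC. A missing Day 1 PUC value has no stated Screening PUC to fall back on, unlike approach 1. Sensitivity Analysis 1, which imputes from Baseline, Day 28 and Day 56, would need redefinition.

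A count of PUC-replaced values by arm and visit would help a reader, but that is extra reporting, not the repair of an error.

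**Conclusion.** The concern does not hold. The mixing of methods is real, but for the hypotheses tested it brings the estimate closer to PUC than Friedewald alone would, or leaves it exactly there. The remaining distance is at most about 3 points under an assumed 8 mg/dL difference and at most 0.75 points under 2 mg/dL, against a planned difference of 30 points. Significance against placebo is not at risk. Sensitivity Analyses 2 and 3 use the same kind of model on the two measures, so the effect of the method will be visible in the report.

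The sizes rest on assumed baselines and offsets. The documents give no Friedewald-PUC difference, so neither the direction nor the size of any bias is shown. The exact-zero result needs only that the methods agree above 50 mg/dL. Which of the two planned measures should be called primary is a matter of judgement, and approach 1 follows the LDL-C definition in Protocol Section 7.

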5.3 Randomization and Blinding

Participants who meet all eligibility criteria will be randomized into the study. Participants will be randomized in a 1:1:1 ratio to the 5 mg obicetrapib, 10 mg obicetrapib, or placebo treatment groups. At randomization, participants will be stratified according to their Screening Visit (Visit 1) LDL-C level (≥100 or <100 mg/dL). An automated interactive response technology (IRT) system will be used to assign the participant to 1 of the 3 treatment groups.

Participants, Investigators, the CRO, and the Sponsor will be blinded to all lipid results from Day 1 (Visit 2) for the first participant through database lock in order to protect blinding to treatment assignment.

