#### 2.2.4 Sample Size Determination

A sample size of at least 108 evaluable participants (ie, 36 participants per treatment group) will provide >90% power to detect a 30% difference in LDL-C reduction at Day 56 (standard deviation of 15%) for each of the obicetrapib groups compared to the placebo group at a 2-sided significance level of 0.025.

The sample size for this study was determined in order to provide sufficient power for the analyses of the primary efficacy endpoint described above. Therefore, assuming an approximately 5% dropout rate, enrollment of approximately 114 participants (ie, 38 participants per treatment group) is planned for this study. This sample size will also contribute sufficient participant exposure and safety data.

Participants will be stratified according to their Screening Visit (Visit 1) LDL-C levels (≥100 or <100 mg/dL).

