#### 3.4.2 Secondary Efficacy Endpoints

Similar MMRM models as described for the primary efficacy analyses will be used to analyze the secondary efficacy endpoints. No adjustment will be made for multiplicity in testing the secondary efficacy endpoints. Nominal p-values will be provided when applicable. The following endpoints will be examined:

- Percent change from Day 1 to Day 56 in ApoB for each obicetrapib group compared to the placebo group;
- Percent change from Day 1 to Day 56 in non-HDL-C for each obicetrapib group compared to the placebo group; and
- Percent change from Day 1 to Day 56 in HDL-C for each obicetrapib group compared to the placebo group.

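### The primary model adjusts only for Day 1 LDL-C and leaves out the Screening LDL-C that stratified randomization; validity is unaffected, but a little precision is lost

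*SAP*

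**What the plan says.** Protocol section 5.3 (repeated in SAP 2.2.2) says that at randomization "participants will be stratified according to their Screening Visit (Visit 1) LDL-C level", with a cut at 100 mg/dL.

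SAP 3.1.3 sets a general rule: "Baseline will be defined as the last measurement prior to the first dose of study drug". On visit days the dose follows the fasted blood draw, so for LDL-C this is normally the Day 1 sample. The schedule of procedures places Screening 1 to 14 days before that.

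SAP 3.4.1 fits an MMRM with treatment, visit, their interaction and continuous Baseline. It explains that stratification served only to balance LDL-C across arms, and that "the MMRM model will include the original scale of the LDL-C value as a continuous covariate, not categorical". Protocol 9.2.1.1 lists the same terms, so the two documents agree. The ANCOVA sensitivity analyses use treatment and Baseline LDL-C. No described model contains the stratum or the Screening value.

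For the secondary endpoints, SAP 3.4.2 says only: "Similar MMRM models as described for the primary efficacy analyses will be used to analyze the secondary efficacy endpoints". SAP 3.4.3 treats the other lipids the same way. Neither section names the baseline covariate.

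**The concern.** The SAP's reason would be complete if the stratum were a coarse version of the covariate. It is not, because the two come from separate draws. Day 1 LDL-C also divides the outcome: a Day 1 reading that is high by chance makes the percent change look more negative. Adjusting for Day 1 LDL-C removes part of that error but cannot separate a high reading from a truly high level. A second pre-treatment reading helps to do so, and the Screening lipid profile already supplies one.

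What is at stake is the width of the intervals for each dose against placebo. Protocol 1.4 says the data will support dose selection, so interval width matters beyond rejecting zero. For the secondary lipids there is also a gap in specification, since the covariate is left to inference.

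**Working it through.** **1. The plan's own figures.** SAP 2.2.4 gives: "A sample size of at least 108 evaluable participants (ie, 36 participants per treatment group"; "provide >90% power to detect a 30% difference in LDL-C reduction at Day 56"; a "standard deviation of 15" percent; and the test "for each of the obicetrapib groups compared to the placebo group at a 2-sided significance level of 0.025".

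- SE of a difference: 15 × √(2/36) = 3.54 points.
- Standardized effect: 30/3.54 = 8.49. The critical value is 2.24, so power = Φ(8.49 − 2.24) = Φ(6.24), above 99.99%.
- For 90% power: n = 2 × (15/30)² × (2.24 + 1.28)² = 6.2, so 7 per arm.
- Detectable difference at 90% power with 36 per arm: (2.24 + 1.28) × 3.54 = 12.5 points.
- Enrolment: 108/0.95 = 113.7, so 114; 36/0.95 = 37.9, so 38.

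The stated figures hold.

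**2. Why Day 1 does not use up the Screening information.** On the log scale, let a person's true level have variance s² and each reading have error variance e². The percent change contains −(Day 1 error).

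- Error variance left after adjusting for Day 1: v = e²s²/(e² + s²).
- Error variance left after adjusting for Day 1 and Screening: w = e²v/(e² + v).

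Assumptions: s = 0.28; pooled within-arm SD 15 points (variance 0.0225 on the proportion scale); effects of 0, 30 and 40%. Day 1 error then scales by 1, 0.7 and 0.6 across the arms (mean 0.767). A single common coefficient recovers 0.767² = 0.588 of the drop v − w. The residual variance with Day 1 in the model is 0.0225 − 0.588(e² − v). The extra term takes the residual degrees of freedom from 104 to 103.

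| CV | v | w | 0.588(v − w) | Residual variance, Day 1 only | Variance cut | SE cut after 1 df |
|---|---|---|---|---|---|---|
| 5% | 0.00242 | 0.00123 | 0.00070 | 0.02245 | 3.1% | 1.1% |
| 8% | 0.00592 | 0.00307 | 0.00167 | 0.02222 | 7.5% | 3.4% |
| 10% | 0.00887 | 0.00470 | 0.00245 | 0.02184 | 11.2% | 5.3% |

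**3. Simulation of the same mechanism.** This used a Day 56 ANCOVA as a stand-in for the MMRM, with 36 per arm, blocks of 6 within strata, median LDL-C 95 mg/dL and SD 15. The table gives the change in the model SE relative to Day 1 only.

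| CV | + stratum | + continuous Screening LDL-C |
|---|---|---|
| 5% | 0.1% larger | 1.0% smaller |
| 8% | 0.4% smaller | 3.1% smaller |
| 10% | 1.2% smaller | 5.1% smaller |

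A wider grid of 16 settings (CV 6–12%, between-person log-SD 0.2–0.3, response SD 6–10 points) gave cuts of 0.1–2.7% for the stratum and 2.7–7.1% for the Screening value. In the four settings with an outcome SD near 15, the Screening value cut the SE by 4.2–7.0%. Taking CVs of 5–10%, the working range is about 0–2.6% for the stratum and 1–7% for the Screening value.

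**4. In practical units.** A 95% half-width before multiplicity adjustment is 1.96 × 3.54 = 6.93 points. A 1–7% cut narrows it by 0.07–0.49 points. The equivalent sample-size gain is 1/0.99² = 1.02 to 1/0.93² = 1.16, that is, 2–16%.

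**5. Secondary lipids, if each model holds only its own baseline.** Assumptions: own baseline correlates with LDL-C at 0.85–0.95 for ApoB and non-HDL-C, and at −0.1 to 0.2 for HDL-C; the response correlates with LDL-C at 0.1–0.3.

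| Endpoint | SE cut, + stratum | SE cut, + continuous LDL-C |
|---|---|---|
| ApoB, non-HDL-C | 0.0–0.2% | 0.0–1.3% |
| HDL-C | 0.2–1.9% | 0.5–4.7% |

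**The case against.** The choice is declared and reasoned. The stratified analyte is in the primary model, in a form that carries more information than a two-level cut. A reader might infer that leaving out the stratum invalidates the primary test. It does not. In a simulation of the Day 56 model with continuous Baseline, type I error at nominal 0.025 was 0.023–0.025, and model SEs matched empirical SEs. That simulation used generic correlations, without Day 1 error in the denominator, and the stratum brought no gain at all: SEs of 3.54, 3.41 and 3.18 with or without it, at prognostic correlations of 0.1, 0.3 and 0.5.

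Most of the gain comes from the continuous Screening value, which is not itself the stratification factor. Respecting the randomization does not require it. Its size depends on a visit-to-visit CV that the documents do not give, and with power above 99.99% a 2–16% sample-size equivalent changes no decision on the primary test.

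A reader might also infer that the secondary models carry no LDL-C term. SAP 3.4.2 does not say that. Own-endpoint baseline is the natural reading, but the covariate is not named, and the example MMRM code is missing from the text available for review, so it cannot settle the matter. Nor do the documents show that HDL-C response depends on LDL-C.

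All of this stands, and it limits the point to a minor one. It leaves two things in place: the stated rationale treats two measurements as one, and a second pre-treatment reading goes unused.

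**Conclusion.** The point holds as a minor improvement. Screening LDL-C determines the strata, Day 1 LDL-C is the only LDL-C covariate described, and the SAP's reason for leaving out the stratum overlooks that these are separate draws. The primary analysis is valid and its power is not in question. Under assumed CVs of 5–10%, the stratum recovers roughly 0–2.6% of the standard error, and nothing at the low end, where the lost degree of freedom cancels it. Continuous Screening LDL-C recovers about 1–7%. Claims of a large or guaranteed gain, of a biased test, or of secondary models known to lack LDL-C go beyond the documents. For ApoB and non-HDL-C the expected gain is near zero. For HDL-C it is at most a few percent, and only if its response depends on LDL-C.

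**What to change.** Before unblinding:

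- **Primary MMRM and ANCOVA sensitivity models:** add continuous Screening LDL-C alongside Baseline LDL-C or, at the least, the IRT stratum. Define the Screening value as the one the IRT used to stratify, because Protocol 4.3 and 4.4 allow retests and rescreening.
- **Secondary and other lipid MMRMs (SAP 3.4.2 and 3.4.3):** state that the covariates are the lipid's own baseline plus the randomization stratum.
- **Rationale in SAP 3.4.1:** say that Screening and Day 1 LDL-C are separate measurements.
- **SAP section 5:** record the added term, since Protocol 9.2.1.1 lists only the baseline value.

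The cost is one degree of freedom per model and an SAP edit. No new data are needed.
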